3.2c. Control group considerations: Current evidence suggests “usual care” dietary interventions in primary care settings are either absent (only 20% of patients with CVD, diabetes, or dyslipidemia receive clinic-based nutrition counseling),⁷⁷ ineffective,⁵ or minimally effective (1.2 kg weight loss at 24 months).³ However, given Task Force recommendations and ethical considerations for patients who enroll in a weight loss study, control participants will be offered a weight loss program of an intensity consistent with Task Force guidelines (WW™). It will be given free of charge, similar to the experience of the intervention group. Given prior success of weight loss interventions given in primary care settings^{3,5} and by commercial programs,⁴ we anticipate weight loss at 24 months in our control group will not exceed 1.0% of initial body weight. As noted by Wadden,⁵ weight loss in the control groups of studies conducted in primary care was typically < 0.5%, even among control participants who received augmented usual care.⁷⁸ As we recognize there will be some overlap in dietary pattern between intervention and control groups, we propose objective (skin carotenoids) and rigorous self-reported measures of dietary intake in both groups to assess the degree of overlap.

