8 STUDY ASSESSMENTS AND PROCEDURES

8.1 ENDPOINT AND OTHER NON-SAFETY ASSESSMENTS

8.1.1: Screening, eligibility assessment, and consent

- Outlined in detail in Section 5.5, Strategies for Recruitment and Retention.

8.1.2: Overview of study measures

Study data will be collected at baseline, 4, 12, and 24 months. Process data for the intervention group (Med-South Weight Loss Program) will be collected as part of the intervention via the web-based platform and via REDCap questionnaires completed by counselors immediately after counseling sessions. Process data for the enhanced usual care group will be assessed via a Data Use Agreement with WW™ and by questionnaire at follow-up visits. *As recommended by NIH, our measures include ADOP^T¹³⁷⁻¹³⁹ core constructs (in blue) and specific instruments (in blue underlined) as noted in the Table.*

Primary and Secondary Aims 1 and 2:

Table 3: Outcomes/ Measures	Collection Time (min)	Data collected times (months)				Comment
		0	4	12	24	
Weight (primary outcome) , by electronic scale as the average of two measures, and height (baseline only). SECA 874 dr scales will be used and assessed monthly for accuracy with standardized weights..	5	x	x	x	x	At study outset, seven standardized 50 lb. weights certified for accuracy by NC state standards lab.*
Secondary Outcomes						
Objective measures						
--Blood pressure by noninvasive automated monitor (Omron HEM-907XL, Vernon Hills, IL) with a first measure after seated for 5 minutes and 2 repeat measures at 1-minute intervals	10	x	x	x	x	
--Blood work: performed by LabCorp 
Fasting lipid panel: total cholesterol, triglycerides, HDL, and calculated LDL and VLDL. If participants are unable to fast a non-fasting sample is collected with non-fasting stat notedA1cOther chemistry: glucose, ALT, creatinine (if not previously checked in prior 2 years and only at baseline), and CRP	10	x	x	x	x	Creatinine collected at baseline for those without measure in preceding 2 years.

--blood work: preformed in lab of [name]. Serum and plasm specimens are frozen to – 80 C. immediately after collection and processing. • interleukin (IL)-6, tumor necrosis factor (TNF)-alpha, and C-reactive protein (C-RP)						
--skin carotenoids, Reflection Spectroscopy Device ("Veggie Meter"™) ¹⁴⁰⁻¹⁴²	5	x	x	x	x	

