Participant skin carotenoids will be assessed using a pressure-mediated reflection spectroscopy (RS) device (Veggie Meter®). RS uses broad-band white light to measure skin carotenoids directly through their respective absorptions from 400-750 nm. Reflected light is routed to a spectrograph coupled with a room-temperature detector array. The RS device measures finger skin tissue and adjusts for potentially confounding effects of melanin and hemoglobin. Participants will clean their hands with soap and water, the right index finger will be scanned 3 times and the average value will be used in our analysis. Each scan take ~3 seconds. Regarding RS cross-calibration to ensure comparability across the NC and MN sites, each RS Device comes with a standard calibration method that is used for all devices. In order to assess reliability (reproducibility of the measure), we will use the same strategy used in our small validity paper,⁶¹ wherein RS measures are taken three times in the same person at the same time point, and we will calculate reliability.

To use the Veggie Meter®, the finger is inserted into the instrument’s finger cradle to a) bring the pad of the fingertip in close contact with a light delivering and collecting contact lens, and b) to gently apply pressure to the finger such that blood is temporarily squeezed out of the measured skin region. A laptop computer interfaced to the instrument analyzes the light that is reflected from the finger, and subsequently derives a carotenoid score. The measurement takes 10 or 45 seconds, depending on whether a single- or multiple measurement mode is chosen, respectively. In multiple measurement mode, the finger is inserted and retracted three times and an average score is determined for the three measurements. In this study, we will use single-measurement mode, and will ask participants to insert and reinsert their fingers three times. Since carotenoid levels differ slightly between fingers, always measure the same finger when tracking changes. For this study’s purposes, we will use the right index finger.

Veggie Meter® Supplies and Calibration

1. Supplies

- a. The Veggie Meter® consists of a box shaped base or pedestal that contains the electronics and an oval-shaped housing unit on top of the base that provides an optical interface for the fingertip to be measured (see Figure 4).
- b. Two cables (gray and black)
- c. Laptop
- d. Stopwatch

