Figure 8. Veggie Meter® Dark Reference Stick.

j. After proper positioning, click on the DARK REFERENCE button located in the right panel of the program window. The display panel will now show the reflection spectrum for the dark reference. It should look similar to the spectrum shown below (Figure 9), consisting of a strong peak at about pix number 70 and a weaker, broad band, in the 80-200 pixel number region. The height/intensity of the strong peak which is indicated on the vertical axis should be $\sim 10,000 \pm 500$.

[figure not shown]
- k. Insert the white reference stick into the finger cradle such that the indentation in the white plastic material fits snugly over the contact lens. Make sure the white surface is pointing down.
- l. After proper positioning, click on the WHITE REFERENCE button in the right panel of the program window. A spectrum is displayed that should look similar to the one shown above, but smoother, consisting of a strong peak and a broad band. The intensity of the strong peak should be in the range of 42,000 to 56,000.
- m. Once calibrated, the instrument is ready for skin measurements.
- n. Be sure to calibrate the device after each participant's three readings are completed.

Veggie Meter® Measurement

1. Participant will be asked to wash hands with soap and water prior to measurement.
2. Choose Single Scan mode in the Veggie Meter® display window (we will have participant insert and re-insert finger three separate times, so do NOT choose Average of 3 Scans mode).
3. Enter the participant's ID# into the Subject ID field in the display window. Do NOT enter the participant's name.
4. .
5. Please turn the Veggie Meter computer screen away from the participant to "blind" him/her to the output from the Veggie Meter scan.
6. Ask the participant to insert his/her right index finger. The index finger should be positioned in the cradle such that the finger sits snugly into the indentation (see Figure 10).

7. Click on START. In Single Scan mode, the display window will first flash SCANNING IN PROGRESS, display a progress bar, and after finishing the scan, will show the Carotenoid Score on a scale from 0 to 800 (see Figure 11).
8. In the display panel at the right, the measured score is compared with a histogram of scores for the general population. The histogram region corresponding to the measured score is shown in RED.

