9. Record the Veggie Meter® value (i.e., *Your Carotenoid Score*) BEFORE clicking the Close button! Record all three of the values on the Tanita print out so the participant can review it after all measurements are completed.
10. Click on the Close button to return to the measurements screen and start a new scan.

11. The measurement data are automatically saved in a folder on disk C called ResultsM. A shortcut is placed on the desktop.

12. Note: The average carotenoid score is approximately 200.

Veggie Meter® Troubleshooting

Sometimes the communication between computer and instrument can be lost. In those cases, corresponding measures will appear in the program window. To re-establish communication, exit the program and/or unplug and reconnect the instrument's USB connections and start over.

Veggie Meter® Shut Down

1. After the scores have been recorded for each participant on the data collection form, turn off the power on the Veggie Meter® housing unit (low button in back).
2. In the measurements screen, click on upper right window button (x) to close program window. In following Exit window, click on the OK button.
3. Pull up main computer menu by sliding up on mouse pad, click on "Power" and "Shut down" on the following window.

Stool Collection Protocol added 3/2/20

Stool Collection and Shipping Instructions Important notes:

1. Please read through all instructions before beginning the collection.
2. Please only collect your sample on Sunday, Monday, or Tuesday.
3. Please select a day when you do not have atypical diarrhea or constipation. We are interested in your usual bowel movement.
4. Please ship your sample, or return your sample to the clinic, within 24 hours of collecting your sample.
5. Please contact [study contact], at [study contact phone number], if you have questions or if you will be returning your sample to the clinic.

Your collection kit contains the following items:

- 1 Small shipping container with label (paper towels inside)
- 3 Stool collection tubes with a brown caps
- 3 Larger clear transport tubes with white caps

3 Biohazard bags

1 Stool collection commode kit

1 Water-soluble bag (clear color)

1 Bubble bag (clear color)

1 Pair of disposable gloves (cream-color)

1 Study questionnaire

1 Blue zip-lock bag

How to collect the stool samples:

STEP 1.

- Lift the toilet seat and place the stool collection frame on the back of the toilet bowl.

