- Within 1 week of a measurement visit, the participant's current medications will be printed for review at the visit.
 - At the visit, the list will be reviewed by the RA and medications associated with the above conditions will be confirmed/updated. After the visit, the study medication REDCap form will be completed by the RA.
 - If it is apparent that the participant is unsure about medications and assistance from a clinician is needed to better determine medication use, [name] will be contacted to call the patient within 2 weeks of the visit to clarify medication use.

Adverse outcomes

- We do not anticipate adverse outcomes to be a consequence of the intervention.
- We will however assess for emergency room visits and hospitalizations at each follow-up questionnaire. If the participant responds positive, then per our HIPAA authorization we will review the EHR to confirm primary reason for emergency room visit and/or admission.
- We will categorize emergency room and hospitalizations as follows:
 - Acute myocardial infarction
 - Angina pectoris
 - Stroke
 - Thrombotic
 - Hemorrhagic
 - TIA
 - Heart failure
 - Coronary bypass surgery
 - Cancer
 - Type of cancer
 - Broken bone
 - Type of fracture
 - Light headedness or dizziness
 - Pneumonia
 - Other infection
 - UTI

- Other
- Hypoglycemia
- Other

8.1.5: Study measures returned to participants

Routine study measures that participants can interpret, will be returned to participants, including:

- Weight
- Height
- BMI
- Blood pressure
- Blood lipids: total cholesterol, HDL cholesterol, triglycerides, LDL cholesterol
- A1c

8.1.6: Study measures available to the participants primary care clinician (PCP)

- The PCP will be notified about high blood pressure as outlined above in Section 8.1.3.2: above.
- The lab report from LabCorp will be uploaded in the EHR. The PCP is made aware of this upload. The lab report includes blood lipids (as above), A1c, and C-reactive protein (CRP)

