## **7.2 Key Secondary Outcomes**

Key secondary outcomes include changes in the following outcomes from baseline to 24 months.

- blood pressure
- A1c

- markers of inflammation
- skin carotenoids
- self-reported dietary patterns

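### Veggie Meter step 9 tells staff to give both arms their skin carotenoid scores before the 24-month endpoint, which sits poorly with step 5 and section 8.1.5 and needs reconciling

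*Protocol*

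**What the plan says.** **Return of scores.** In Protocol 8.1.3.4, step 9 of the Veggie Meter measurement procedure reads: "Record all three of the values on the Tanita print out so the participant can review it after all measurements are completed". No arm or visit is excepted.

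**Masking.** Step 5 of the same procedure says "Please turn the Veggie Meter computer screen away from the participant to" keep the result of the scan out of sight. The protocol's own term for this is blinding.

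**Returned measures.** Section 8.1.5 states "Routine study measures that participants can interpret, will be returned to participants, including" weight, height, BMI, blood pressure, lipids and A1c. Skin carotenoids are not listed.

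**Schedule.** Table 3 in section 8.1.2 has a row for "skin carotenoids, Reflection Spectroscopy Device", marked at 0, 4, 12 and 24 months.

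**Role of the measure.** In the control-group paragraph of Protocol 4.2 the investigators expect some dietary overlap between arms and write that "we propose objective (skin carotenoids) and rigorous self-reported measures of dietary intake in both groups to assess the degree of overlap". SAP 7.2 lists "skin carotenoids" among the key secondary outcomes, as change from baseline to 24 months. The SAP does not mention returning scores.

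**The concern.** A score written down for the participant to read is feedback on the quantity being measured. The WW arm is meant to resemble an ordinary referral to WW by a primary care provider (Protocol 6.1.1), and such a referral would not bring repeated carotenoid scores. The Med-South arm already receives counselling on vegetables and fruit. If the two arms act on the score to different degrees, part of the 24-month carotenoid contrast would reflect the measurement procedure and not the two programmes. The assessment of dietary overlap would be affected in the same way.

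At stake is the interpretation of one key secondary outcome, which is the only diet measure that the protocol calls objective. As the text stands, a reader cannot tell whether participants saw that outcome during follow-up.

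**Working it through.** **1. Is the printout needed to capture the data?** No. Step 11 says that the measurements save automatically, the shut-down instructions refer to scores recorded on a data collection form, and the data table in section 10.1.8 has carotenoid values entered in REDCap by field staff. The only purpose that step 9 gives for the printout is review by the participant.

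**2. How many returns could affect the endpoint?** There are four visits (0, 4, 12 and 24 months). The 24-month return follows the 24-month scan and cannot affect it. That leaves 4 − 1 = 3 returns of three values each. The baseline measures precede randomization (section 5.5), but a score seen then could still influence later behaviour.

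**3. Do the three places agree?**

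| Place | Reading A | Reading B |
|---|---|---|
| Step 5 | The participant should not learn the score | Masking applies only while scanning |
| 8.1.5 | The list is complete, so carotenoids are not returned | The list gives examples, so return is not ruled out |
| Step 9 | Contradicts both | Operates as written; both arms receive scores |

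Under A the protocol contradicts itself. Under B it is consistent, but it returns a key secondary outcome before the endpoint without saying so in the section on returned measures.

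**4. Is step 9 meant for this trial?** There is reason for doubt. The introduction to the same procedure contains the phrase "Regarding RS cross-calibration to ensure comparability across the NC and MN sites", whereas this trial recruits in North Carolina only. Step 9 names a Tanita printout, whereas the weight protocol specifies a Seca 874 scale and no Tanita device appears elsewhere. On the other side, the procedure is marked as updated on 1/26/20, before the first enrolment on 6/12/2020. Step 9 also survived the review of the whole protocol recorded as version 1.9 on 6/8/25. It is current text.

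**5. Which way would feedback move the contrast?** Let δ be the Med-South minus WW difference in carotenoid change that the programmes alone produce, and let f_M and f_W be the changes caused by seeing the scores. Then

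observed contrast = δ + (f_M − f_W).

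Taking δ as positive (Med-South higher):

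- f_M = f_W: the contrast is unchanged.
- f_W > f_M: it shrinks.
- f_M > f_W: it grows.

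The documents give no value for either term.

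**6. Does any planned figure change?** Protocol 9.2 and SAP 9.6 give a detectable effect of 0.33 SD for secondary outcomes with 360 participants, 20% attrition, 80% power and α = 0.05. This reproduces:

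- n per arm = 360 × 0.8 / 2 = 144
- detectable effect = (1.960 + 0.842) × √(2/144) = 0.330 SD
- power at 0.33 SD = Φ(0.33 × √(144/2) − 1.960) = Φ(0.840) = 0.80

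No row of Protocol Table 5 names skin carotenoids, so there is no planned carotenoid SD or target difference to adjust. The figure stands.

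**The case against.** The strongest reply is that nothing shows that any score was handed over. The step calls for a printout from a device that the trial does not specify, and the values go to REDCap in any case. The consent pages, which might say which results are returned, are not available for this review. Steps 5 and 9 can also be read together as masking during the scan and review afterwards, and the list in 8.1.5 is introduced in a way that need not be exhaustive. All of this stands. It limits the point to what the text instructs.

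The content of the feedback is thin too. The population histogram appears on the screen turned away from the participant (steps 5 and 8), the average of about 200 is a note in the staff procedure (step 12), and no explanation to participants is described. The protocol already returns weight, blood pressure, lipids and A1c to both arms, so feedback of measurements is not foreign to the design. This bears on how large an effect might be. It does not settle whether carotenoid scores should be returned.

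A reader might infer that feedback biases the contrast toward zero because WW participants learn something new. The documents do not support that. Both arms would get the same numbers. Med-South participants have a counsellor, a session on vegetables and fruit, and goal-setting (section 6.1.2), so they could respond more. WW's dietary content is not described, so it cannot be said that this arm lacks guidance on dietary pattern.

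**Conclusion.** Minor. As written, step 9 directs that participants in both arms be given their scores at baseline, 4 and 12 months, ahead of the 24-month outcome, and this sits poorly with step 5 and section 8.1.5. Whether it happened is unknown.

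If the step was followed, the carotenoid contrast may include a feedback effect. This assumes that participants read the scores, act on them, and do so differently by arm; none of the three is shown. Direction and size are therefore open. Calling the contrast a likely underestimate, or attaching a loss of power to it, would go beyond the documents. The primary outcome, percent weight change, is not shown to be affected.

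**What to change.** Reconcile step 5, step 9 and section 8.1.5 by replacing step 9 with: *Record the three values on the REDCap form only; do not return carotenoid scores to participants until the 24-month visit is complete.*

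If scores were already returned, state to which arms and at which visits, and report this beside the carotenoid result as a possible influence of unknown direction. The SAP is dated 9/10/24, after all participants were randomized, and mentions a review of the analysis in May 2025. The statement of what was actually done is therefore likely to be the more useful part now.

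The cost is one line of the measurement procedure and a sentence or two in the report. The downside is that participants wait until the end of the study for a research score. No analysis model, power figure or sample size changes.

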8.3.4 TIME PERIOD AND FREQUENCY FOR EVENT ASSESSMENT AND FOLLOW-UP

Solicited potential adverse events will occur at each follow-up measurement visit (4, 12, and 24 months). They include the following and we will ask if evaluation for these events included emergency room visit or overnight hospital stay.

- Acute myocardial infarction
- Angina pectoris
- Stroke
 - Thrombotic
 - Hemorrhagic
- TIA
- Heart failure
- Coronary bypass surgery
- Cancer
 - Type of cancer
- Broken bone
 - Type of fracture
- Light headedness or dizziness
- Pneumonia
- Other infection
 - UTI
 - Other
- Hypoglycemia
 - Other

As allowed by our HIPAA authorization, the EHR will be reviewed to confirm the above events and modify the date of occurrence if not accurately provided by the participant. For clinical events that were managed outside of facilities with EHR data available to investigators, we will request that participants sign a release of medical information so that pertinent medical records can be reviewed.

Unsolicited adverse events (AE) or serious adverse events (SAE) may come to the attention of study staff during counseling visits, phone calls, or via other channels of communications. They will be categorized as above and entered into the appropriate follow-up questionnaire at the time of occurrence.

Information to be collected about AEs and SAEs includes event description, time of onset, study clinician's assessment of severity, relationship to study procedures (assessed only by those with the training and authority to make a diagnosis), and time of resolution/stabilization of the event. All AEs occurring while on study will be documented appropriately regardless of relationship. All AEs will be followed to adequate resolution.

Any medical or psychiatric condition that is present at the time that the participant is screened will be considered as baseline and not reported as an AE. However, if the study participant's condition deteriorates at any time during the study, it will be recorded as an AE.

Changes in the severity of an AE will be documented to allow an assessment of the duration of the event at each level of severity to be performed. Documentation of onset and duration of each episode will be maintained for AEs characterized as intermittent.

Study staff will record events with start dates occurring any time after informed consent is obtained until the last day of study participation.

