Stopping rules with regard to statistical power and adverse events	Semi-annual assessment by DSMC. The DSMC will review subject accrual for futility and adverse events for compelling evidence of harm and will address appropriately.

Operational definition of futility with regard to recruitment: Less than one half of the anticipated sample size enrolled during the enrollment period. This may be modified by the voting members of the DSMC.

Meetings and responsibilities of the DSMC: Prior to enrollment, the DSMC will meet to review all protocols that may have a bearing on subject accrual or safety. The DSMC will subsequently meet every 6 months until completion of the study. In addition, the PIs of the study or the Chair of the DSMC may convene additional meetings as needed. The primary role of the DSMC will be to monitor study data as outlined in the table above. The committee will also assist with any necessary modifications of protocols to address unexpected problems with subject accrual, subject attrition, or adverse events.

Measurement and reporting of adverse events (AEs): The study team will monitor adverse events that include, but are not limited to the following: deaths, hospitalizations, emergency room visits, hypoglycemia (defined as blood glucose < 60 mg/d with symptoms), and weight loss greater than 10 pounds per month. We will specifically inquire about these adverse events at all follow-up measurement visits and review medical records to confirm as appropriate (permission granted through HIPAA waiver). The PIs will be responsible for completing an AE report when a reportable adverse event is recognized and will submit this report to the UNC IRB. The UNC IRB definitions, standards, and forms will be used for reporting AEs. Also, at measurement visits, we will inquire about angina, myocardial infarction, transient ischemic attack, and stroke.

Approval of study phases: The intervention will be delivered in 3 phases over 24 months by research staff: Phase I (4 months) focuses on adopting a Med-style dietary pattern; Phase II (8 months) on weight loss; and Phase III (12 months) on weight loss maintenance. In our NIH application, we noted we would continue with intervention refinement until shortly before going to the field with each phase. This will allow us to keep up with the literature and be up-to-date at the outset of each phase. Accordingly, we will seek IRB and DSMC approval for each Phase as outlined in the table below:

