## **9.5 Safety and Tolerability Analyses**

Prior to analysis, any data-captured adverse events will be coded by the principal investigators. Each type of event (by seriousness, severity, relationship to study) will be descriptively summarized in frequency tables by group (including only a single occurrence of any distinct type of event for any participant). The number of CVD events, ER visits, and hospitalizations will also be descriptively summarized by group. No inferential statistics (p-values or confidence intervals) are planned for comparing safety data between groups.

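### Protocol 8.1.4 and 8.3.4 give different entry questions for the same adverse-event list; if the 8.1.4 form was used, events treated outside hospital rest on unsolicited reports, for which Med-South has far more planned contacts than WW

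*Protocol*

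**What the plan says.** Protocol 8.1.4 (Questionnaire data, Adverse outcomes) starts from care use: "We will however assess for emergency room visits and hospitalizations at each follow-up questionnaire". The next step depends on the answer: "If the participant responds positive, then per our HIPAA authorization we will review the EHR to confirm primary reason for emergency room visit and/or admission". The event list follows as a coding scheme: "We will categorize emergency room and hospitalizations as follows".

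Protocol 8.3.4 uses essentially the same list the other way round. The events themselves are solicited: "Solicited potential adverse events will occur at each follow-up measurement visit (4, 12, and 24 months". The care setting is asked about each event: "They include the following and we will ask if evaluation for these events included emergency room visit or overnight hospital stay". The same section adds that unsolicited events "may come to the attention of study staff during counseling visits, phone calls, or via other channels of communications", and has them entered into the follow-up questionnaire.

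The DSMC charter (Protocol 10.1.6) names among its monitored events "hypoglycemia (defined as blood glucose < 60 mg/d with symptoms", and commits to asking about these events at every follow-up measurement visit. It attaches no care-setting condition.

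Table 3 in Protocol 8.1.2 lists adverse outcomes beside CVD events, ER visits and hospitalizations. SAP Table 1 and SAP Appendix A do the same. None of them gives the question asked.

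SAP 9.5, matching Protocol 9.4.4, uses the data as follows: "Each type of event (by seriousness, severity, relationship to study) will be descriptively summarized in frequency tables by group".

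**The concern.** Sections 8.1.4 and 8.3.4 cannot both be a full description of one questionnaire. On the 8.1.4 route, a participant who treated a low glucose at home, or saw a clinician in the office for dizziness, answers no to the entry question, and nothing further is asked about the event. On the 8.3.4 route the same participant reports the event.

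This matters because at least 40% of participants are planned to have diabetes, and hypoglycemia and light-headedness can be managed without an ER visit or admission. If solicitation misses such events, what remains is whatever participants happen to tell staff, and the two arms differ greatly in how often they talk to study staff. An event table by arm built on that basis could look falsely reassuring overall. It could also show a Med-South excess that reflects contact rather than risk.

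**Working it through.** No power or error-rate figure is involved. The check is a comparison of texts and a count of planned contacts.

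**Step 1. The passages side by side.**

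| Place | What opens the enquiry | Role of ER/hospital | Home-treated hypoglycemia | Home-treated dizziness |
|---|---|---|---|---|
| Protocol 8.1.4 | ER visit or admission | Condition for coding a reason | Not solicited | Not solicited |
| Protocol 8.3.4 | The listed event | Further question about the event | Solicited | Solicited |
| DSMC charter, 10.1.6 | The monitored event | Monitored item in its own right | Solicited | Not named |
| Protocol Table 3; SAP Table 1 and Appendix A | Wording not given | Listed beside adverse outcomes | Cannot tell | Cannot tell |

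So 8.3.4 and the charter agree on hypoglycemia against 8.1.4. For dizziness, only 8.3.4 provides explicit solicitation. The EHR review does not clearly close the gap: the Table 3 comment describes it as confirming what the questionnaire collected.

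**Step 2. Planned post-baseline study contacts.**

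- Med-South counseling sessions (SAP 6.5): 4 + 14 + 12 = 30.
- Phase I follow-up calls, one after each of 4 sessions (Protocol 6.1.2): 4.
- Phase II follow-up calls (Protocol 6.1.2): 6 to 12.
- Measurement visits, both arms: 3.

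Med-South low: 30 + 4 + 6 + 3 = 43. Med-South high: 30 + 4 + 12 + 3 = 49. WW: 3, leaving out start-up and scheduling calls.

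Some Med-South sessions coincide with measurement visits; Protocol 6.1.2 places the opening Phase II session at the 4-month visit. If all three coincided, the distinct occasions would be 43 - 3 = 40 to 49 - 3 = 46. The contrast with 3 is unchanged in substance. These are planned contacts, not attended ones.

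**Step 3. What the contacts imply.** Study counseling exists only in Med-South, and its Phase II content includes safety advice for people on diabetes or blood-pressure medication, a natural prompt for such reports. In WW, Protocol 6.1.1 says the study does not actively promote participation after start-up, and the data feed described in 6.2.1 lists attendance, weights, logins, diet and activity but no adverse events. If the three shared visits asked only about ER and hospital use, the occasions for an unprompted report would lie mostly in one arm.

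**Step 4. Whether the planned tables would show it.** Unsolicited events go into the same follow-up questionnaire, and SAP 9.5 does not separate them from solicited ones. A contact-driven difference would therefore not be visible.

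**The case against.** The strongest reply is that 8.1.4 never says ER visits and hospitalizations are the sole things asked. It can be read as describing one component of a wider item, since the measures tables list adverse outcomes separately. Section 8.3.4 is the dedicated adverse-event section, and with the charter it solicits hypoglycemia in both arms whatever the care setting. On that reading there is a drafting inconsistency and no loss of data. This stands as a possibility. The documents do not show which form was fielded, so the consequence can only be stated conditionally.

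Three stronger inferences should be resisted.

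- A reader might infer that WW participants have no way to report such events. They do: phone calls and other channels in 8.3.4 are open to both arms, and WW participants attend the same three visits, each with a medication review by staff.
- A reader might infer that the DSMC would see only extreme hypoglycemia. That would require 8.1.4 to override the committee's own charter, and Protocol 8.3.5 sends other AEs to the chair monthly without a care-setting limit.
- A reader might want a count of missed events. It would need rates of glucose-lowering drug use, of hypoglycemia and of ER attendance, none of which the documents give.

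It is also fair that unequal unsolicited contact exists under 8.3.4 as well, so changing the entry question alone would not remove it. That supports separate tabulation.

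**Conclusion.** The inconsistency is real and should be resolved, with a conditional consequence. If the 8.1.4 form was the one used, listed events handled outside an ER or hospital would be captured only as unsolicited reports, and the planned opportunity for such reports is about 43 to 49 contacts in Med-South against 3 in WW. The by-group adverse-event tables could then undercount these events and differ between arms because of contact. The direction rests on the contact schedule and on the unsolicited route in 8.3.4; how much reporting would differ is not documented. If the 8.3.4 form was used, solicitation was equal in both arms and only the unsolicited part remains unbalanced.

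Safety summaries are descriptive, with no p-values or confidence intervals planned, and the primary analysis is unaffected. The point is worth correcting because it bears on what may be said about safety.

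**What to change.** 1. Reconcile Protocol 8.1.4, Table 3, 8.3.4 and the DSMC charter to one solicitation text, put identically to both arms: each listed event first, then where it was treated. State which form was actually fielded.
2. In SAP 9.5, tabulate solicited and unsolicited events separately by arm, with events treated in an ER or hospital as a subset.
3. If only the 8.1.4 form was used, title the tables *events leading to ER visit or hospitalization* and make no overall statement about hypoglycemia or dizziness.

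The cost is small: a clarification in the protocol, one additional split in the safety tables and possibly a changed title. The split requires that the source of each report can be recovered from the records. Rewording the questionnaire may come too late. The SAP is dated 9/10/24, after all participants were randomized, and the last protocol review is dated 6/8/25. The disclosure and the table changes can still be made.
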